### **Overview of Intervention and RCT Design:**

As shown below in **Figure 2**, to test the aforementioned hypotheses, we propose to conduct a single-site, assessor-blinded RCT at the WRJ VAMC comparing PEACE plus standard psychiatric hospital discharge care to standard psychiatric hospital discharge care alone. The trial will enroll patients 18 years and older who are being discharged from the WRJ VAMC inpatient mental health unit (called Ground East, GE). The primary aim is to determine whether PEACE reduces suicidal ideation at one, three, and six months after psychiatric hospitalization. The secondary aim is to determine the mechanism by which PEACE exerts its anti-suicidal effect after hospitalization. An exploratory aim includes describing the number of suicide attempts after discharge.

**Baseline Assessment and Randomization:** Prior to the start of study enrollment, allocation cards will be prepared using a fixed-block randomization scheme. These cards will be put into sealed, opaque, numbered envelopes. The box of envelopes will be stored in a locked cabinet in the study coordinator's locked office.

The study team member will meet with each eligible patient in a private room on GE at the WRJ VAMC around the time of discharge. The study team member will obtain informed consent from the patient and then administer the baseline assessments, which are described under the outcome measures (see below). The baseline visit will take approximately 90 minutes to complete. Study staff will also contact the support person the patient selected to obtain consent from this person.

After obtaining consent and completing the baseline assessments, the study coordinator will take the next numbered envelope from the box (described above) and open the envelope to determine the patient's assignment. In the event that the patient has been assigned to the intervention, the study coordinator will notify the intervention staff in order that the intervention staff can initiate the intervention. Otherwise, the patient will be informed that they have been assigned to usual care.

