AES = App Engagement Scale; BHS = Beck Hopelessness Scale; BSS = Beck Scale for Suicidal Ideation; CSSR-S = Columbia Suicide Severity Rating Scale; INQ-15 = Interpersonal Needs Questionnaire-15; M = months; MINI = MINI International Neuropsychiatric Interview; MSPSS: Multidimensional Scale of Perceived Social Support; N/A = Not applicable; SRCS: The Suicide-Related Coping Scale; \*Time is described in minutes

**Baseline Characteristics:** We will collect socio-demographic data from patient report and the electronic medical record such as age, sex, marital status and service history (e.g., branch, era, combat exposure). We will also collect diagnostic information using the MINI International Neuropsychiatric Interview (MINI), which has been validated against the Structured Clinical Interview for Diagnostic and Statistical Manual of Mental Disorders (DSM). The MINI is a short, structured diagnostic interview that, on average, takes about 15 minutes to administer. We will inquire about any history of suicide attempts using the validated Columbia Suicide Severity Rating-Scale (C-SSRS). The C-SSRS includes a 7-item subscale that assesses for actual and interrupted suicide attempts.

**Primary Outcome (Suicidal Ideation):** The primary outcome will be assessed using the Beck Scale for Suicidal Ideation (BSS). Patients will be asked about their current suicidal ideation (i.e., past week) at assessments 1 as well as at assessments 2, 3, and 4. The BSS is a self-reported questionnaire that assesses severity of suicidal ideation. The BSS measures attitudes, behaviors, and plans to die by suicide. Each item on the BSS is scored on a scale from 0 to 2 and the first 19 of the 21 items are used to calculate a total score ranging from 0 – 38. The BSS has high reliability and is a valid measure of suicidal ideation. There is also evidence that the BSS is measurement invariant across time. The BSS is widely used in clinical trials, is sensitive to clinical change, and unlike most other measures of suicidal ideation, higher scores on the BSS are associated with death by suicide. While there is no established BSS cutoff score to classify suicide risk as

high, low, or none, there is evidence that higher scores on the BSS correspond to more severe suicidal ideation. There is evidence that an improvement of five points or more on the total BSS scores may be clinically relevant.

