
suicide risk.

**Secondary Outcome (Suicide Attempts):** We will assess for non-fatal and fatal suicide attempts at one and three months after discharge using the C-SSRS. The C-SSRS is a valid and reliable scale that includes a seven-item subscale that asks patients to self-report on actual attempts, interrupted attempts, aborted attempts, and preparatory acts or behaviors. The scale asks the assessor to document the actual and potential lethality of these behaviors. The C-SSRS is widely used in the VA. The psychometrics of the C-SSRS in Veterans is unknown. We will also review suicide behavior reports (SBR) in the electronic medical record. SBRs are required in the VA and include information on suicide attempts, suicide deaths, and other types of suicidal behaviors including interrupted attempts.

[figure not shown]
**Secondary Outcome (App engagement):** Several measures have been selected to aid in a planned secondary analysis of the data to characterize the relationship between app engagement and outcomes in patients assigned to the intervention arm. Although mHealth is being used with increasing frequency to address various health behaviors, there is a dearth of evidence on effective methods to assess app engagement, though many approaches exist. Therefore, we will administer the App Engagement Scale (AES) at one-, three-, and six- months. Notably, the one- and three-month AES assessment will include the period during which the patient is receiving the PEACE intervention; however, the six-month assessment will measure whether the Veteran decided to continue to use the app on their own even after the intervention period ended and the intervention staff member was removed from the social network. The AES is adapted from the end-user version of the Mobile Application Rating Scale (uMARS). The AES has been studied in patients with mental health conditions, has been shown to have good internal reliability, and is strongly related to app engagement.

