**Figure 5. Timeline of Assessments and Interventions**

dy = days; m = months; MH = Mental health; SDP = Standard psychiatric discharge practices; T0, T1, T2, T3 = assessment time points; wk = weeks

assessment) (3M) and assessment 4 (occurs six months after baseline assessment) (6M). These assessments will be conducted by the independent outcome assessor. The independent outcome assessor will conduct the baseline assessment in a private office on GE. We anticipate that, in most cases, assessment 1 will occur on the day before discharge. Depending on patient preference, the independent outcome assessor will conduct assessments 2, 3, and 4 in a private office on the WRJ VAMC campus, over the phone, or using VA Video Connect. The assessors will be blinded to study assignment and the patients will be instructed to not reveal their status to the assessor. All outcome variables will conform to the PhenX Common Data Elements (CDE) in order to improve our ability to compare our findings across other studies and maximize the impact of our results. The independent assessor will be blinded to study assignment. At each study visit, we will ask the assessor to guess the study assignment of the participant. We will consider that the blinding of the assessor was successful if the assessor is able to guess the assignment less than half of the time.

- Because app engagement will only be tracked in patients exposed to PEACE, we will ask that the study coordinator or study therapist (rather than the outcome assessor) administer the self-reported scale (AES) in order to avoid compromising the blinding of the outcome assessor. Quantitative measures of app engagement can be directly downloaded onto a secure server.
- As the WRJ VAMC is a rural medical center that serves a large geographic area (New Hampshire and Vermont), we anticipate that several enrolled patients will prefer phone (or VA Video Connect) over in-person follow-up. Fortunately, the assessment instruments that we selected for this study can be administered over the phone or in person. Furthermore, our decision to allow patients to participate in study follow-up by phone (or VA Video Connect) or in person is consistent with the study methods of the original WHO BIC trials.

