### Sample Size:

Based on a pilot RCT of the VA BIC Program in 19 patients discharged from the WRJ VAMC inpatient mental health unit (manuscript currently under review), we found that the intervention had an estimated effect size of 0.5 (Cohen's  $d_s$ ) on the BSS. We see the 0.5 as a medium sized effect and consistent with effects of other psychosocial interventions. We have reason to believe that this effect size may be even higher in our trial where we will be

enhancing the intervention with the addition of the mHealth app. We used these pilot data to re-calculate the required sample size for this proposed study. In doing so, we used a formula for

Table 3. Sample size estimates

Power	Alpha	$p$	n	Effect Size	Size of Effect	Intervention	Control	Intervention	Control
0.8	0.05	0.5	4	0.3	Small	109	109	120	120
0.8	0.05	0.5	4	0.5	Medium	40	40	46	46
0.8	0.05	0.5	4	0.6	Medium	27	27	30	30
0.8	0.05	0.5	4	0.8	Large	16	16	18	18

*p = correlation of repeated measures; n = 4 timepoints; N=number*

*\*Size of effect are based on criteria described in Laken D 2013.*

estimating sample sizes for longitudinal designs with repeated measures as proposed by Hedeker et al (1999). We assumed that the correlation of repeated measures ( $p$ ) was 0.5 based on findings from our pilot data. Furthermore, we assumed that there were four assessment points and that the data followed a normal distribution. We made this latter assumption because our pilot data followed a normal distribution according to the Shapiro-Wilk test for normalcy. We also are assuming that the data that we collect in this proposed trial will follow a normal distribution because the data will be drawn from the same population (and the same setting) as our pilot work. As shown in **Table 3**, based on the aforementioned calculations, a sample size of 80 (40 per arm) will achieve an 80% power to detect an effect size of 0.5 (Cohen's  $d$ ) or greater between arms across the study timepoints with a significance level of 5%. In our pilot study, there were no patients who dropped out, but

two patients had missing data at one or three-month follow-up. Conservatively, we assumed that in the proposed trial that there could be a drop out as high as 10%. This means that we will need to recruit for this proposed trial a sample size of **92** (46 per arm).

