## **Resources Available**

This project will be conducted at the WRJ VAMC. We anticipate that we will enroll up to 160 subjects over a period of four years to reach the target sample size of 92 subjects. [name] will oversee and lead this project with the help of research staff, which includes:

- Intervention staff
- Study coordinator(s)
- A statistician
- Independent assessor(s) blinded to study arm

Of note, because this trial is occurring as part of a career development award, [name] will receive ongoing mentorship and support from her mentorship team in conducting this trial. Her primary mentor is [name] who is responsible for overseeing the mentorship team..

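### The rule for judging assessor blinding puts its cut-off at the chance level, so intact blinding fails it at least half the time under a forced two-way guess

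*Combined protocol and SAP*

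**What the plan says.** The trial is a single-site, assessor-blinded comparison of two arms, "comparing PEACE plus standard psychiatric hospital discharge care to standard psychiatric hospital discharge care alone" (Overview of Intervention and RCT Design). The target is 46 patients per arm, 92 in total (Sample Size).

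The check on assessor blinding is in the Study Design section, in the text after Figure 5: "At each study visit, we will ask the assessor to guess the study assignment of the participant". The criterion follows: the investigators will consider "blinding of the assessor was successful if the assessor is able to guess the assignment less than half of the time".

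The documents supplied give no response options for the guess and no handling of don't-know answers. They do not say whether the rule applies per visit, per assessor or to all guesses pooled. Resources Available allows for more than one assessor: "Independent assessor(s) blinded to study arm". Statistical Considerations does not mention the check, so it adds no margin, interval or test.

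**The concern.** A blinding check should separate guesses that carry information about the arm from guesses that do not. With two equal arms and a forced choice, guesses without information are right half the time on average. This rule puts its cut-off at exactly that value, allows no sampling error and treats exactly half correct as not successful. Intact blinding would therefore often be reported as not achieved.

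Three further points add to this:

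- The rule looks in one direction only. Accuracy well below 50% counts as success, although it also departs from chance.
- The verdict depends on choices that are not stated: the response options, the denominator and the level of pooling.
- Read literally, each study visit includes baseline, but allocation happens later: "After obtaining consent and completing the baseline assessments, the study coordinator will take the next numbered envelope from the box". A baseline guess is made before there is an assignment to detect, so it says nothing about blinding and would dilute a pooled figure.

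Patients and therapists cannot be blinded, so assessor blinding is a main safeguard of the design, and this is its only stated check. The stake is the credibility of that statement in the report. The primary test is not at risk: "The BSS is a self-reported questionnaire that assesses severity of suicidal ideation", and none of the analyses for Aims 1 to 3 uses the verdict. Assessor judgement enters mainly through interview ratings such as the C-SSRS, where "The scale asks the assessor to document the actual and potential lethality of these behaviors".

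**Working it through.** **Inputs.** Two arms, 46 per arm, 92 patients (Sample Size). For attrition, "we assumed that in the proposed trial that there could be a drop out as high as 10" per cent, which leaves about 92 × 0.9 = 82.8, so 82 or 83 guesses at a follow-up visit. Three visits after randomisation (1, 3 and 6 months) give at most 92 × 3 = 276 pooled guesses. Assumption: the guess is a forced choice between two arms.

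**The plan's own figures.** The documents give no error rate for the blinding rule, so there is none to reproduce. The sample size that fixes the number of guesses does reproduce closely. The repeated-measures formula gives 2(1.96 + 0.84)² × (1 + 3 × 0.5) / (4 × 0.5²) = 39.2, so 40 per arm as stated. Then 40 / 0.9 = 44.4, so 45 per arm against the stated 46. I use the stated 92.

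**Formula.** Let X be the number correct among n guesses, X ~ Binomial(n, p), with guesses treated as independent. The criterion is met if X < n/2 and missed if X ≥ n/2. With perfect blinding p = 0.5, and by symmetry:

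- n odd: P(missed) = 0.5 exactly;
- n even: P(missed) = 0.5 + ½ P(X = n/2).

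At n = 92, P(X = 46) = 0.083, so P(missed) = 0.5 + 0.0415 = 0.5415.

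**Perfect blinding, forced choice**

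| Guesses | P(criterion missed) |
|---|---|
| 92 | 0.541 |
| 83 | 0.500 |
| 82 | 0.544 |
| 276 (pooled) | 0.524 |

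If the criterion had to be met at each of three visits with 92 independent guesses, a blinded assessor would miss it at least once with probability 1 − (1 − 0.5415)³ = 0.90.

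**Don't-know answers kept in the denominator, n = 92.** With a fraction d of don't-knows, p = 0.5(1 − d) under perfect blinding. If 60% of definite guesses are correct, p = 0.6(1 − d).

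| d | Missed, perfect blinding | Missed, 60% of definite guesses correct |
|---|---|---|
| 0 | 0.541 | 0.980 |
| 0.05 | 0.353 | 0.928 |
| 0.10 | 0.195 | 0.809 |
| 0.20 | 0.033 | 0.389 |

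The same rule therefore ranges from mostly false alarms to mostly missed unblinding, depending on how often assessors decline to guess.

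**Below-chance guessing.** At n = 92 and p = 0.3 under forced choice, the criterion is met more than 99.9% of the time.

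**The alternative.** The exact (Clopper-Pearson) 95% interval includes 0.5 for 37 to 55 correct of 92, and for 33 to 50 of 83.

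| | n = 92 | n = 83 |
|---|---|---|
| Departure from chance if correct count is | ≤ 36 or ≥ 56 | ≤ 32 or ≥ 51 |
| False departure, p = 0.5 | 0.047 | 0.048 |
| Power, p = 0.6 | 0.477 | 0.441 |
| Power, p = 0.3 | 0.977 | 0.963 |

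Within a single arm of 46, power at p = 0.6 is only 0.192.

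**The case against.** Six points can be made in defence of the plan.

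- **The forced choice is an assumption.** This stands as a condition. The instruments are in a separate Assessment Manual that was not supplied and may contain the guess form. The alternative does not rescue the rule, because its error rates then depend on the share of don't-knows.
- **At least half is not quite universal.** It is exact for coin-flip guessing or equal arms. With 41 and 42 patients retained and an uninformed assessor who names the smaller arm 70% of the time, the miss rate is 48%. The exception is real and small.
- **The plan never says unblinded.** Correct: it defines only when blinding is successful. A reader will still take a missed criterion as failed blinding.
- **The rule errs on the cautious side.** Under forced choice it flags 60% accuracy 98% of the time, against 48% for the interval. This is true, but a flag that also goes up 54% of the time with perfect blinding tells the reader little.
- **Nothing downstream depends on it.** This stands, and it limits the importance of the point. Suicide attempts, where the lethality ratings belong, are exploratory and mainly descriptive.
- **Three intervals raise multiplicity.** At 92 guesses the chance of at least one false departure is 1 − (1 − 0.047)³ = 13% if visits are independent. That is worth a note in the report and is far below the 90% for the present rule applied at each visit.

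**Conclusion.** The concern holds. As written, the rule gives a wrong blinding conclusion at least half the time when blinding is intact: 54% at 92 guesses, 50% at 83 and 52% for 276 pooled. This rests on a forced two-way guess, equal arms and, for the exact percentages, independent guesses. If don't-knows are allowed and kept in the denominator, the false-failure rate falls and so does the ability to detect real unblinding, so the rule has no fixed meaning until the response options are stated. Under forced choice the fault lies mainly in false declarations of failure. Sample size, alpha and the primary analysis are unaffected. The rule should be changed, because the trial could otherwise report that its assessor blinding failed when it did not.

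**What to change.** Delete the success criterion from the Study Design section and put the following in its place and in Statistical Considerations:

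- Use only the guesses at 1, 3 and 6 months.
- State the response options. If don't-know is allowed, report its count separately and compute the proportion correct among definite guesses.
- At each visit, report the overall proportion correct with an exact 95% confidence interval, compared with 50% in both directions. Describe guesses as departing from chance when the interval excludes 50%. With 92 definite guesses that means 36 or fewer, or 56 or more, correct; with 83, 32 or fewer, or 51 or more. The limits should follow the actual count.
- Report the proportion by arm as description only. An assessor who favours one label will be above 50% in one arm and below it in the other without any information.
- Do not read an interval that includes 50% as proof of blinding. If visits are pooled, allow for correlation within patients. A blinding index by arm is optional.

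This costs one or two sentences in the protocol and SAP and needs no new data. The price is the loss of a simple pass/fail label and limited power: a true 60% correct would be detected 48% of the time at 92 guesses and 44% at 83.

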**Figure 2. Flow chart of study procedures**

d=days; IC = inclusion criteria; m= months; MH = inpatient mental health; w = weeks

visit) over the course of the three months after psychiatric hospitalization. At each of these contacts, the study therapist will monitor the patient's symptoms, assess treatment adherence, review the safety plan with the patient, and, if necessary, assist the patient with engaging in care. The contacts will include the use of MI techniques. The contact sessions are systematic and structured. The contacts are designed to be highly interactive, allowing times for questions and providing patients with written materials that they can keep for future reference. Depending on the patient's preference, the contacts will be delivered via phone, VA Video Connect, or in-person in a private office on the grounds of the WRJ VAMC.

- ***mHealth Component:***
- As described in the VA BIC manual, the intervention staff member directs patients to a wide variety of resources available within and outside the VA that may assist them in their recovery after discharge. One of these resources includes the My3App to help with suicide prevention in veterans. The app is a free app available for Android or iPhone and is owned and maintained by Vibrant Emotional Health, the administrator of the National Suicide Prevention Lifeline.

[figure not shown]
While the My3App has been endorsed by the VA, the app has not been formally tested in Veterans and is not currently incorporated in a standard fashion in discharge care practices. The intervention staff member will introduce the app as part of the brief educational intervention and will provide formal education around the role of the app in follow-up care. The interventionist will continue to encourage use of the app at each follow-up visit.

1) ***Behavioral health coach:*** The study therapist will educate patients on My3 during the brief educational visit and set up the app on the patient's phone. In this study, the study therapist will act in the role of behavioral health coach and therefore, in this role, their VA-issued iPhone number will be added to the patient's app. In their role as "Coach," the study therapist will be available to the patient between follow-up visits to answer any question and facilitate mental health treatment engagement. If My3 app were to be implemented into routine practice, the "Coach" would be a mental health provider (e.g., suicide prevention coordinator (SPC)).

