**Specific Aim 3:** We plan to conduct an exploratory analysis on the number of suicide attempts (fatal and non-fatal) that occur after discharge in the intervention plus standard psychiatric hospitalization discharge care arm compared to standard psychiatric hospital discharge care, alone. While suicide deaths and suicide attempts are important clinical endpoints, this single-site trial will not be powered to detect a statistically significant effect between study arms. Furthermore, because we assume that few events will be observed in either arm, we plan to summarize our findings by providing basic descriptive statistics regarding the number of events in each arm at one-, three-, and six-month follow-ups. In the event that there are a sufficient number of suicide attempt events to perform statistical analysis, we will use a log-rank statistic to test for statistically significant differences in the proportion of suicide attempts between arms. We will use the Kaplan-Meier method to plot and compare survival curves for each arm. Specifically, we will calculate the time from the baseline assessment (assessment 1) to first suicide attempt after discharge for each study arm. Patients who are lost to follow-up or do not attempt suicide will be censored during the analysis. We will calculate hazard ratios using the Cox proportional hazards model. This approach will also enable us to adjust for baseline differences between study arms, if necessary. We plan on using these data to inform a future trial that is powered to detect an effect.

**Proposed Secondary Analysis:** Within the intervention group, we will conduct a secondary analysis of engagement with the mHealth app to assist further in the interpretation of our findings. Specifically, we are interested in learning about the degree to which patients assigned to PEACE interacted with app and whether differences in the degree of engagement with the app are associated with changes in social connectedness and suicidal ideation. First, we will generate descriptive summary statistics (e.g., means and standard errors, medians) and graphical displays for app engagement at one and three-month follow-up. Second, we will use generalized linear modeling to evaluate the relationship between app engagement and the primary outcome, suicidal ideation, and the secondary outcome, social connectedness.

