### **Protected Health Information:**

We will administer several validated instruments to all enrolled patients at baseline and follow-up (one-, three- and six-month follow-ups). These instruments ask various questions related to self-harming thoughts or behavior and social connectedness. We will also ask patients to report on any non-VA healthcare utilization at one-, three- and six- month follow-ups. Demographic data and other baseline characteristics will be collected from the patient's electronic medical record at baseline. Information on VA healthcare utilization will be collected from the patient's electronic medical record at one- and three-month follow-ups. For patients assigned to the intervention arm, data on app utilization will also be downloaded from their app. All data will be collected solely for the purposes of this study. All study data will be collected using an electronic data-capture system. These data are stored on a local, secure research server that only study staff will have access to. All paper copies of study-related data, including consent and HIPAA forms, will be kept in a locked file cabinet, in a locked office, dedicated to this study. Only research staff will have access to this locked cabinet.

The My3 app will not store any PHI within the app. The app will only require access to the patient's contact list in order to facilitate a phone call between the patient and their support person.

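### The study therapist, who coaches patients on the app, may also administer the App Engagement Scale: an avoidable risk of socially desirable answers in a secondary, within-arm analysis

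*Combined protocol and SAP*

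**What the plan says.** **Who gives the scale.** The bullets after Figure 5 in the Study Design section state "we will ask that the study coordinator or study therapist (rather than the outcome assessor) administer the self-reported scale (AES"). The purpose given is "in order to avoid compromising the blinding of the outcome assessor". No rule chooses between coordinator and therapist, and nothing requires a record of who gave the scale.

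**The therapist's role in the app.** Under the mHealth Component of the PEACE Intervention Description, the therapist teaches the patient to use My3, sets it up on the phone, and has a VA-issued number added to it: "the study therapist will act in the role of behavioral health coach". The same section adds: "The interventionist will continue to encourage use of the app at each follow-up visit". The patient keeps the same therapist for eight contacts, the initial visit plus seven.

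**When and how it is used.** Table 2 schedules the AES at 1, 3 and 6 months. Under Secondary Outcome (App engagement), the six-month score is meant to show whether the Veteran kept using the app unprompted, after the intervention ended and the staff member left the app's network. The Proposed Secondary Analysis, confined to the intervention group, plans descriptive summaries at 1 and 3 months and then "we will use generalized linear modeling to evaluate the relationship between app engagement and the primary outcome", with social connectedness as a second outcome.

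**Objective data.** The Study Design section also says "Quantitative measures of app engagement can be directly downloaded onto a secure server", and the Protected Health Information section says that for intervention patients "data on app utilization will also be downloaded from their app".

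**The concern.** The AES is a self-report of how engaging the patient finds the app. If the therapist gives it, the patient answers to the person who installed the app, appears in it and has been urging its use. That is a recognised setting for answers that please the questioner.

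The stake is the reading of the app component. The secondary analysis is there to help interpret the trial by asking whether patients who engaged more with the app also changed more in connectedness and suicidal ideation. Inflated ratings would make uptake look better than it was. If patients with a stronger bond to the therapist inflate more, and also do better because of the contacts themselves, part of that benefit would be credited to the app.

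**Working it through.** The plan gives no figure on this point, so there is none to reproduce. The check has three steps.

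**1. Does the stated reason require the therapist?** Protecting the assessor's blinding excludes the assessor only. Under Baseline Assessment and Randomization, "the study coordinator will take the next numbered envelope from the box", opens it, and notifies the intervention staff when the patient is assigned to PEACE. The coordinator therefore already knows the arm and can give the AES without affecting blinding. The therapist option serves no purpose that the coordinator does not.

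**2. How many scores are exposed?** The Sample Size section gives 46 patients per arm and allows for 10% dropout.
- Upper limit: 46 × 3 = 138 scores, if the therapist gives every AES and nobody is lost.
- With 10% dropout: 46 × 0.9 = 41.4, so about 41 patients and 41 × 3 = 123 scores.
- Lower limit: 0, if the coordinator always gives it.

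**3. What would inflation do to the planned model?** This is an illustration; apart from the patient number, the inputs are assumptions, not values from the documents. Take 41 patients, true engagement E and rapport A independent with SD 1, and no true relation between E and the outcome.

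- *Uniform inflation.* The recorded AES is E + 0.5. In 5,000 simulated trials the mean AES rises by 0.50 SD, the slope stays at about 0 (−0.002), and the test rejects in 5.0% of trials, against 5.2% with no inflation. Levels shift; the association does not.
- *Inflation that varies with rapport.* The recorded AES is E + b + bA, and A correlates 0.3 with the outcome. The expected false slope is covariance over variance, 0.3b / (1 + b²).

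| b (SD of inflation per SD of rapport) | Expected slope | Simulated slope | Rejection at 5% level |
|---|---|---|---|
| 0.25 | 0.075 / 1.0625 = 0.071 | 0.066 | 7.0% |
| 0.5 | 0.15 / 1.25 = 0.120 | 0.120 | 13.0% |
| 1.0 | 0.30 / 2 = 0.150 | 0.147 | 25.8% |

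The formula and the simulation agree. Inflation as such does not bias the association; inflation tied to a correlate of outcome does. Under these assumptions the false-positive rate runs from slightly above nominal to about five times nominal.

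**The case against.** The strongest reply has four parts.

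- **Objective usage data are planned.** The text on app engagement speaks of several measures, and the analysis section does not name the AES as its only predictor. This stands as mitigation, not as a cure: Table 2 lists only the AES for app engagement, no usage metric is defined, and the Proposed Secondary Analysis does not say which measure enters the model.
- **Rapport would confound the association whoever holds the form.** A patient who likes the coach may truly use the app more and also improve. This stands in full. Changing the administrator removes only the extra reporting bias. The coordinator is also unblinded study staff, so some socially desirable answering could persist.
- **Exposure may be small.** The coordinator is named first, and by six months the therapist has left the app's network, which weakens the motive to please. This stands in part: nothing bars the therapist from giving the six-month AES, the score meant to show use without the coach.
- **The consequence is minor.** This stands. The analysis is secondary and within one arm; suicidal ideation and connectedness are collected by the blinded assessor.

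A reader might also infer that administration will in fact vary between patients and visits. The documents permit either person; they do not say that both will be used or that they will alternate.

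**Conclusion.** The point holds as a low-severity, avoidable measurement risk. The plan permits the app's coach to collect the self-reported engagement score, and its stated reason does not need that permission. Descriptive engagement levels could be inflated. The within-arm association could be distorted only if the inflation varies with something related to outcome.

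The size is unknown. The 7% to 26% rejection rates are conditional on an assumed 0.3 correlation between rapport and outcome and on assumed degrees of rapport-dependent inflation; they are not estimates for this trial.

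A reader might go further and conclude that the AES results are biased, or that the trial's main finding is at risk. The documents support neither. No bias is demonstrated, the coordinator may turn out to give every scale, and the randomised comparison, the primary outcome and the sample size do not depend on the AES.

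**What to change.** 1. In the Study Design section, delete the three words that allow the therapist to give the AES. The coordinator then gives it, or has patients complete it themselves, at 1, 3 and 6 months.
2. Record who administered any AES already collected. The Secondary Outcome (Patient Engagement) text refers to data already reviewed from the trial, so some scores may exist.
3. In the Proposed Secondary Analysis, define one downloaded usage measure before the data are examined, and report its summaries and its association with suicidal ideation and connectedness beside those of the AES.

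The cost is a short protocol edit and a small amount of added coordinator time; the documents give no coordinator workload, so that should be confirmed. No new staff role is needed and assessor blinding is unchanged. Because confounding by true rapport with the therapist remains, the association should still be reported as observational.
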